9.1.2.2 Maintenance Period

During the Maintenance Period of the Core Study (up to 12-week), subjects will continue taking perampanel oral suspension once daily at the dose level they achieved at the end of the Titration Period. (revised per Amendment 02) Multiple dose adjustment is allowed if a subject is experiencing intolerable AE(s) or a higher dose is deemed to be beneficial. All visits are to be done within ± 7 days of the schedule. Each study visit is based on the actual prior visit (eg, Visit 6 is completed 3 weeks ± 7 days of Visit 5, Visit 7 is completed 4 weeks ± 7 days of Visit 6, Visit 8 is completed 4 weeks ± 7 days of Visit 7, Visit 9 is completed 4 weeks ± 7 days of Visit 8). (revised per Amendment 02)

During the Titration and Maintenance Periods, all dose adjustments will be done via 1 dose level up or down. Those who cannot tolerate a minimum of 2 mg dose must discontinue from the study.

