ABNAS = A-B neuropsychological assessment schedule, AE = adverse event, AED(s) = antiepileptic drug(s), β-hCG = beta-human chorionic gonadotropin (or hCG = human chorionic gonadotropin), C-SSRS = Columbia-Suicide Severity Rating Scale, eCRF = electronic case report form, EQ-5D-Y = EuroQol 5 Dimensions-Youth, fT3 = free triiodothyronine, fT4 = free thyroxine, IGF-1 = insulin-like growth factor-1, IxRS = interactive and response system, PK = pharmacokinetics, TSH = thyroid-stimulating hormone.

Table 4 Schedule of Procedures/Assessments in Study E2007-G000-311: Core Study

Phase	Pre-Treatment	Treatment Phase									Early Discontinuation ^d	Unscheduled
	Screening/Baseline	Titration ^a				Maintenance ^b				Follow-up ^{b,c}		
Visit	1	2	3	4	5	6	7	8	9			
Week	From up to -4 weeks ±3 days to Week 0 (outside of Japan) -4 weeks ±3 days to Week 0 (Japan only) (revised per Amendment 02)	0	2	5	8	11	15	19	23	27		
Procedures/Assessments												

- a: All visits to be done within ±3 days of the schedule. Each study visit is based on the actual prior visit (eg, Visit 3 is completed 2 weeks ±3 days of Visit 2, Visit 4 is completed 3 weeks ±3 days of Visit 3, Visit 5 is completed 3 weeks ±3 days of Visit 4). (revised per Amendment 02)
- b: Visit to be done within ±7 days of the schedule. Each study visit is based on the actual prior visit (eg, Visit 6 is completed 3 weeks ±7 days of Visit 5, Visit 7 is completed 4 weeks ±7 days of Visit 6, Visit 8 is completed 4 weeks ±7 days of Visit 7, Visit 9 is completed 4 weeks ±7 days of Visit 8). (revised per Amendments 02 and 03)
- c: The Follow-up Visit only applies to those subjects who complete the Core Study (or who discontinue the study early), but do not roll-over into Extension A and is to occur 4 weeks (±7 days) after Visit 9 or last dose of study drug.
- d: These assessments will be conducted for subjects who discontinue the study early for any reason after Visit 2.
- e: Physical and neurological examinations will only be performed at Visit 1 and Visit 9 and at the Follow-up Visit, and at the Early Discontinuation Visit (if applicable). For all other clinic visits during the study, the physical and the neurological exams will only be performed when there is a complaint from the subject. Clinically significant abnormal findings from the physical or the neurological examinations will be reported as AEs.
- f: Blood pressure and pulse will be taken.

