#### 5.1.2 Secondary Endpoints

The following endpoints will be analyzed:

1. The relationship between plasma levels of perampanel and efficacy endpoints (ie, change in average seizure frequency over 28 days, responder probability, and the proportion of subjects who are seizure-free in the Maintenance Period of the Core Study) separately for each seizure type
2. The relationship between plasma levels of perampanel and cognition endpoints including change from baselines in ABNAS, CBCL, and LGPT. In addition, depending on the AE data, the relationship between plasma levels of perampanel and select AEs will be assessed
3. Change from baseline at Week 23 and Week 52 in ABNAS, CBCL, and LGPT
4. Changes from baseline at Week 23 and Week 52 in growth and development parameters (height, weight, thyroid, and IGF-1)
5. Change from baseline in EEG and the frequency of EEG abnormalities during awake and sleep state
6. Proportion of subjects (aged 6 or older at time of consent/assent) with any treatment-emergent reports of suicidal ideation and behavior on the C-SSRS and intensity of these behaviors assessed using C-SSRS scores
7. The median percent change in seizure frequency per 28 days during Treatment Phase (Titration Period and Maintenance Period) of the Core Study, and during the long-term treatment (up to 52 weeks) relative to the Pretreatment Phase. Seizure frequency will be based on the number of seizures per 28 days, calculated as the number of seizures over the entire time interval divided by the number of days in the interval and multiplied by 28
8. Proportion of responders (25% responders defined as a decrease in 28-day seizure frequency of equal or greater than 25% compared to baseline seizure frequency; 50% responders defined as a decrease in 28-day seizure frequency of equal or greater than 50% compared to baseline seizure frequency; 75% responders defined as a decrease in 28-day seizure frequency of equal or greater than 75% compared to baseline seizure frequency) during Maintenance Period of Core Study, and during the long term treatment (up to 52 weeks)
9. Proportion of subjects who are seizure-free during Maintenance Period of Core Study, and during the long-term treatment (up to 52 weeks)
10. CGI of Change

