### 8.2.2 Treatment Duration for Safety Analyses

The treatment duration for non-AE safety variables is same of non-diary efficacy analysis in 8.1.2 Treatment Duration for Efficacy Analyses. For AEs, the treatment duration is considered to begin on Day 1 and ends 28 days after the last dose of treatment phase .

The post-treatment duration is considered to begin on the day after the treatment duration for safety. Since it is not always possible for all study participants to come in for their clinic visits on the exact day specified in the protocol schedule, the visit week of a subject's visit will be based on the actual visit occurring during the treatment duration. These visits will be used to create by visit summaries for laboratory, vital signs, electrocardiograms and other safety analyses data. The end of treatment value is the last non-missing value in the treatment duration.

Any concomitant medication taken within the 14 days after the last dose data will be listed/summarized as part of the concomitant medication listing/table.

AEs for the subject were collected and reported on CRF starting from the time subject signed informed consent to the last visit in the Treatment Phase following subject's last dose. Serious AEs were collected for 28 days after the last dose.

For summaries of safety by time points, the time points will be relative to date of first dose. For standardized reporting, study day windows relative to the first dose (Day 1) in the study will be applied to determine into which week the data will be mapped. Scheduled, unscheduled, and early withdrawal visits will be mapped to weeks. Table 2 below gives the mapping of relative day ranges to week for non-AE safety variables. If a subject did not have a recorded observation falling within a given range of days in order to be assigned to a week, the subject's data for that week will be regarded as missing for summarization purposes. If there are two or more assessments in the same window then:

- if the window is the baseline assessment, then the latest assessment will be used in the summary tables;
- if the window is the follow-up assessment, then the latest assessment will be used in the summary tables;

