**Table 1: Mapping of Study Day Ranges to Week**

Windowing Period	Study Day Range (Relative to First Dose)	Week
Pretreatment	Day $\leq 1^a$	0
Treatment	$2 \leq \text{Day} \leq 25$	2
Treatment	$26 \leq \text{Day} \leq 46$	5
Treatment	$47 \leq \text{Day} \leq 67$	8
Treatment	$68 \leq \text{Day} \leq 88$	11
Treatment	$89 \leq \text{Day} \leq 119$	15
Treatment	$120 \leq \text{Day} \leq 147$	19
Treatment	$148 \leq \text{Day} \leq 175$	23
End of Treatment(EOT) of Core Study	-	b
Follow up for completer of Core Study	$176 \leq \text{Day} \leq 203$	c
Follow up for discontinuation of Core Study	After the date of discontinuation $\leq \text{Day} \leq \text{last dose of study drug} + 35$	

- a: All assessments performed on the same date as the date of first dose were to be performed prior to dosing; results from these assessments will be regarded as Pretreatment values in the analyses.
- b: The last non-missing value measured in the Treatment Phase will be handled as the data of EOT of the Core Study. The Follow-up visit will not be included in this analysis visit.
- c For the safety assessment other than AE, the data assessed as the planned visit of the Follow-up will be handles as those of Follow-up visit. AE occurred on or after the date of discontinuation will be handles as that of Follow-up period.

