### 8.2.3 Handling of Replicate Data

A subject having an AE coded to the same preferred term more than once during the study will be counted only once in the incidence calculations for that AE. Similarly, if a subject has more than one AE in a single body system, the incidence will be counted only once for that body system. If a subject has the same AE more than once, the occurrence that is of greatest severity will be used in the calculation of the incidence of individual AE by severity. Similarly, the AE considered most closely related to study drug will be used in the calculation of incidence of individual AE by relationship.

For the laboratory, vital signs, ECG and other safety variables datasets, the measurement noted as the scheduled visit measurement will be used in the analysis. If more than one assessment is present at a scheduled visit, then the nearest assessment for evaluation

visit(day) will be used in the summaries of the actual values and changes from baseline. In the event of two assessments being equally close to the scheduled visit day, the last assessment will be used.

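### Core visits are timed from the previous actual visit but both SAPs map scheduled visits to weeks by fixed days from first dose, so a compliant Visit 9 can miss the Week 23 window, and neither SAP says which of its visit rules prevails

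*SAP*

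**What the plan says.** **Protocol.** Sections 9.1.2.1 and 9.1.2.2 and the notes to Table 4 chain the Core visits: "Each study visit is based on the actual prior visit". The intervals are "Visit 3 is completed 2 weeks ±3 days of Visit 2, Visit 4 is completed 3 weeks ±3 days of Visit 3", then "Visit 5 is completed 3 weeks ±3 days of Visit 4", then "Visit 6 is completed 3 weeks ±7 days of Visit 5, Visit 7 is completed 4 weeks ±7 days of Visit 6". Visits 8 and 9 each follow 4 weeks after the one before, within 7 days. Titration is given a length of at most 11 weeks and Maintenance at most 12.

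**Both SAPs.** Section 8.2.2 of the Core SAP and of the Extension SAP says that "study day windows relative to the first dose (Day 1) in the study will be applied" to place data in weeks. It extends the mapping to scheduled as well as unscheduled and early-withdrawal visits, and treats a week with no observation in its range as missing. Week 23 is Days 148 to 175 in Core Table 1 and in Extension Table 6. Days 120 to 147 are Week 19. Days 176 to 203 form the Core row "Follow up for completer of Core Study"; Days 176 to 208 are Week 28 in the Extension SAP.

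**Other rules in the same documents.** Section 8.2.2 of each SAP also says that the visit week rests on the actual visit. Core SAP 8.2.3 adds that "the measurement noted as the scheduled visit measurement will be used in the analysis"; the Extension SAP has no counterpart to that sentence. Core Table 1, footnote b, keeps the last Treatment Phase value as end of treatment. Footnote c reserves the Follow-up label for non-AE data collected at the planned Follow-up visit.

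**Endpoints.** Section 5.1.2 of both SAPs names "Change from baseline at Week 23 and Week 52 in ABNAS, CBCL, and LGPT", and next the Week 23 and Week 52 changes in height, weight, thyroid and IGF-1.

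**The concern.** A chained schedule lets permitted deviations accumulate; a window counted from first dose does not move with them. The further a child is into the Core Study, the more likely it is that a visit within protocol lands in a neighbouring window. Visit 9 is the last of seven links and is the visit that supplies the Week 23 endpoint.

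If the day-window rule is applied as written, some children who followed the protocol have no Week 23 value. In Table 4, CBCL, height, thyroid and IGF-1 have no other scheduled on-treatment assessment in the Core Study, so nothing else can fill the gap. For weight, which is measured at every visit, the wrong visit can fill it: with Visit 8 on Day 150 and Visit 9 on Day 178, the Visit 8 weight becomes the Week 23 weight.

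If the actual-visit or scheduled-visit wording is applied instead, the same children are counted in Week 23. Two programmers working from the same SAP could therefore produce different Week 23 tables.

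**Working it through.** **1. Reproduce the nominal day.** Visit 2 is Day 1. Intervals from Protocol Table 4, notes a and b: 14 + 21 + 21 + 21 + 28 + 28 + 28 = 161 days. Visit 9 is therefore Day 1 + 161 = Day 162, which is Week 23 as in Table 4. The lower edge of the SAP window also fits: the midpoint of the nominal Visit 8 and Visit 9 days is (134 + 162)/2 = 148.

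**2. Accumulate the tolerances.** Visits 3 to 5: 3 × 3 = 9 days. Visits 6 to 9: 4 × 7 = 28 days. Total 37 days.
- Earliest compliant Visit 9: 162 − 37 = Day 125.
- Latest: 162 + 37 = Day 199.
- If the 11-week and 12-week period lengths are hard caps, the latest is 1 + 77 + 84 = Day 162, and the range is Days 125 to 162.

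**3. Map to the SAP windows under the day-window rule.**

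| Compliant Visit 9 | Number of days | Core SAP | Extension SAP |
|---|---|---|---|
| Days 125–147 | 23 | Week 19 | Week 19 |
| Days 148–175 | 28 | Week 23 | Week 23 |
| Days 176–199 | 24 | no Week 23 value; kept as end of treatment | Week 28 |

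So 23 + 24 = 47 of the 75 permitted days lie outside Week 23. Had Visit 9 been anchored to Day 1 with a 7-day tolerance, it would fall on Days 155 to 169, wholly inside the window. The mismatch comes from the chaining.

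**4. How much drift is needed.** Two days late at each of the seven visits gives 162 + 14 = Day 176, one day past the window. Three days early at each gives 162 − 21 = Day 141, in Week 19.

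**5. Frequency, by assumption.** The documents hold no visit-timing data. Deviations are taken as independent and uniform on whole days, with no cap on period length. The distribution of their sum is computed exactly, and the share with Visit 9 on or before Day 147 or on or after Day 176 is read off.

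| Assumed deviations | Early | Late | Outside Week 23 |
|---|---|---|---|
| Full windows (±3, ±7) | 6.1% | 7.5% | 13.6% |
| Half windows (±1, ±3) | <0.01% | 0.01% | 0.01% |
| Half windows, mean delay 1 day per visit | 0 | 6.4% | 6.4% |
| Half windows, mean delay 2 days per visit | 0 | 55% | 55% |

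With the planned 160 children all reaching Visit 9, 13.6% is 0.136 × 160 ≈ 22. Symmetric scatter matters little unless the full windows are used. Consistent lateness matters a great deal, because seven small delays add up.

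**The case against.** The strongest reply is that the SAPs already provide for this. Section 8.2.2 of both says the visit week follows the actual visit, and Core 8.2.3 uses the scheduled-visit measurement. A reader might infer from the day-window sentence alone that compliant values will certainly be misassigned. The documents do not support that: they contain both rules and rank neither. But the reply does not settle the matter the other way. The actual-visit sentence does not say whether it means the visit number or the visit date, the mapping sentence names scheduled visits explicitly, and Core 8.2.3 sits under replicate data and claims no precedence.

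Three further limits stand.
- It is tempting to say that a late Core Visit 9 is relabelled as Follow-up, because it falls in that row's day range. Footnote c confines the label to data from the planned Follow-up visit, so the value has no week label.
- It is tempting to say that the data are lost. In the Core analysis footnote b keeps the value as end of treatment; it is lost from the Week 23 summary only. The Extension SAP's end of treatment is the last value of its own Maintenance Period, so a child with later data has no such fallback there.
- EEG might be thought affected too, but Core SAP 5.6.6 sends it to a separate plan and the EEG endpoint names no Week 23.

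The late branch also depends on whether the period lengths are hard caps. The revision history for Amendment 02 ties the wording to flexibility in line with the visit windows, which favours the uncapped reading without proving it. With hard caps the early branch remains.

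Finally, fixed day windows are a legitimate choice and the affected summaries are descriptive. That limits the consequence but does not resolve the conflict between the rules.

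**Conclusion.** The point holds as a conflict between the visit schedule and the week mapping, with an unresolved order of precedence inside the SAPs. The range of Days 125 to 199 and the window of Days 148 to 175 are exact. Under the day-window rule, compliant Visit 9 values drop out of the Week 23 summaries of ABNAS, CBCL, LGPT, height, thyroid and IGF-1, and the Week 23 weight may be missing or come from Visit 8.

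The number of children affected cannot be read from the documents. It runs from practically none (half windows, no drift) through 13.6% (full windows, uniform) to about 55% (half windows, mean delay of 2 days per visit). These figures rest on independent deviations and no cap on period length; the documents supply no basis for choosing among them. The change should be made: it is cheap, it can alter the Week 23 tables, and it concerns endpoints that the plan names.

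**What to change.** In Core SAP 8.2.2 with Table 1, and in Extension SAP 8.2.2 with Table 6, state that:
- scheduled visits are assigned to weeks by CRF visit number (Visit 9 = Week 23, Visit 10 = Week 28, and so on);
- this rule takes precedence over the day windows;
- the day windows apply only to unscheduled and early-withdrawal assessments.

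This agrees with the direction of Core SAP 8.2.3; the Extension SAP should carry the same sentence.

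The cost is SAP wording and one programming rule, with no new data. The trade-off is a wider spread of actual days under one label: in theory Days 125 to 199 for Week 23, a span of 75 days against 28 now. That matters most for growth measures, which change with time. Listing the actual study day makes the spread visible, and a sensitivity summary restricted to Days 148 to 175 can be added if wanted.

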**Table 1: Mapping of Study Day Ranges to Week**

Windowing Period	Study Day Range (Relative to First Dose)	Week
Pretreatment	Day $\leq 1^a$	0
Treatment	$2 \leq \text{Day} \leq 25$	2
Treatment	$26 \leq \text{Day} \leq 46$	5
Treatment	$47 \leq \text{Day} \leq 67$	8
Treatment	$68 \leq \text{Day} \leq 88$	11
Treatment	$89 \leq \text{Day} \leq 119$	15
Treatment	$120 \leq \text{Day} \leq 147$	19
Treatment	$148 \leq \text{Day} \leq 175$	23
End of Treatment(EOT) of Core Study	-	b
Follow up for completer of Core Study	$176 \leq \text{Day} \leq 203$	c
Follow up for discontinuation of Core Study	After the date of discontinuation $\leq \text{Day} \leq \text{last dose of study drug} + 35$	

- a: All assessments performed on the same date as the date of first dose were to be performed prior to dosing; results from these assessments will be regarded as Pretreatment values in the analyses.
- b: The last non-missing value measured in the Treatment Phase will be handled as the data of EOT of the Core Study. The Follow-up visit will not be included in this analysis visit.
- c For the safety assessment other than AE, the data assessed as the planned visit of the Follow-up will be handles as those of Follow-up visit. AE occurred on or after the date of discontinuation will be handles as that of Follow-up period.

### 8.2.3 Handling of Replicate Data

A subject having an AE coded to the same preferred term more than once during the study will be counted only once in the incidence calculations for that AE. Similarly, if a subject has more than one AE in a single body system, the incidence will be counted only once for that body system. If a subject has the same AE more than once, the occurrence that is of greatest severity will be used in the calculation of the incidence of individual AE by severity. Similarly, the AE considered most closely related to study drug will be used in the calculation of incidence of individual AE by relationship.

For the laboratory, vital signs, ECG and other safety variables datasets, the measurement noted as the scheduled visit measurement will be used in the analysis. If more than one assessment is present at a scheduled visit, then the nearest assessment for evaluation

visit(day) will be used in the summaries of the actual values and changes from baseline. In the event of two assessments being equally close to the scheduled visit day, the last assessment will be used.

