- g: Weight and Height (without shoes) will be measured. Three measurements should be taken at each visit. Each measurement should be recorded as a separate entry on the Vital Sign eCRF.
- h: Only for those subjects who continue into Extension A.
- i: Unused study drug to be retrieved and study drug dispensed only for subjects requiring dose increases at Unscheduled Visits.
- j: Clinical laboratory tests include hematology, blood chemistry including lipid panel, and urinalysis.
- k: Fasting lipid and glucose samples to be taken at baseline and at end of treatment or early discontinuation, with fasting window (interval) between 2 and 4 hours.
- l: Female subjects age 8 years old and above, or of childbearing potential, only. If urine can not be obtained for pregnancy testing after screening, a serum pregnancy test will be performed. (revised per Amendment 01)
- m: Only for subjects aged 6 years and older at the time of consent/assent.
- n: If subject has a normal ECG baseline reading, but during any visit thereafter, the QT is measured as greater than 450 ms, 3 consecutive ECGs separated by 5 to 10 minutes will be performed to confirm the abnormality.
- o: During Unscheduled Visits, ECG or EEG will only be done if the results from the previous visit were deemed clinically significant by the investigator.
- p: EEG will be performed at awake and sleep state for all subjects.
- q: One blood sample (approximately 1 mL) for determination of perampanel plasma concentrations will be collected at any time during each of the specified visits.

Table 4 Schedule of Procedures/Assessments in Study E2007-G000-311: Core Study

Phase	Pre-Treatment	Treatment Phase									Early Discontinuation ^d	Unscheduled
	Screening/Baseline	Titration ^a				Maintenance ^b				Follow-up ^{b,c}		
Visit	1	2	3	4	5	6	7	8	9			
Week	From up to -4 weeks ±3 days to Week 0 (outside of Japan) -4 weeks ±3 days to Week 0 (Japan only) (revised per Amendment 02)	0	2	5	8	11	15	19	23	27		
Procedures/Assessments												

- r: Additional blood (approximately 1 mL/sample) will be drawn at the 1st report (where possible) of a serious adverse event or severe unexpected AE and at its resolution. (revised per Amendment 01)

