#### 5.6.4 Vital Signs

Descriptive statistics for vital signs parameters (ie, systolic and diastolic BP, pulse, respiratory rate, temperature, weight) and changes from baseline will be presented by visit.

In addition, the criteria described in the table below will be used to determine clinically notable results for blood pressure and heart rate. The number (percentage) of subjects with clinically notable results over all scheduled and unscheduled visits will be summarized.

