If the window is not the baseline or the follow-up assessment, then the assessment closest to the scheduled assessment will be used in the summary tables. Note that if two assessments are equidistant from the scheduled assessment then the last assessment of the two (within the allowable window) will be used.

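### Core SAP 8.2.3 limits laboratory, vital-sign and ECG analyses to scheduled-visit measurements without restricting that rule to by-visit summaries, in conflict with SAP 5.6.3, 5.6.4, 5.6.5 and 8.2.2

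*SAP*

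**What the plan says.** Core SAP 8.2.3 (Handling of Replicate Data) states for the laboratory, vital-sign, ECG and other safety datasets that "the measurement noted as the scheduled visit measurement will be used in the analysis". Its next sentence deals with several assessments at one scheduled visit. There the nearest one is chosen, and the choice is tied to a purpose: it "will be used in the summaries of the actual values and changes from baseline".

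Other parts of the Core SAP read differently:

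- **8.2.2, mapping:** "Scheduled, unscheduled, and early withdrawal visits will be mapped to weeks".
- **8.2.2, several assessments in one window:** outside the baseline and follow-up windows, "the assessment closest to the scheduled assessment will be used in the summary tables". This paragraph is introduced as applying to safety summaries by time point.
- **8.2.2, end of treatment:** "The end of treatment value is the last non-missing value in the treatment duration".
- **5.6.4:** the number of subjects with "clinically notable results over all scheduled and unscheduled visits will be summarized".
- **5.6.3:** shift tables run to the highest and lowest postbaseline value, a TEMAV is a qualifying postbaseline value, and the ALT, AST and bilirubin summaries are also given for the maximum over the treatment duration. None of these names a visit type.
- **5.6.5:** the QTc table counts subjects with one or more abnormal postbaseline ECGs in the treatment period, again with no visit type.

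Protocol Table 4 places on-treatment Core laboratory tests at Weeks 11 and 23 and the on-treatment ECG at Week 23. Both are also listed at Early Discontinuation and Unscheduled visits. Unscheduled laboratory tests carry no trigger. For unscheduled visits, note o says that "ECG or EEG will only be done if the results from the previous visit were deemed clinically significant by the investigator".

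**The concern.** Section 8.2.2 names scheduled, unscheduled and early-withdrawal visits as three kinds. A rule that admits only the scheduled-visit measurement therefore reads naturally as excluding the other two. The authors limited the second sentence of the 8.2.3 rule to actual values and changes but left the first unlimited. Section 5.6.4 names unscheduled visits where they are wanted, and 5.6.3 and 5.6.5 do not. A programmer could take that difference as deliberate and derive the highest postbaseline value only from records that 8.2.3 admits.

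Laboratory, vital-sign and ECG parameters are components of the primary safety endpoint (SAP 5.1.1). The tables at stake are TEMAV, shift to highest and lowest value, ALT/AST/bilirubin multiples, Hy's Law, clinically notable vital signs and QTc categories. These tables exist to find extremes, so leaving out values taken between planned visits works against their purpose.

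**Working it through.** The plan states no figure on this point. The check is a comparison of passages plus the direction of any effect.

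**1. Is there a conflict?** Take an on-treatment value from an unscheduled visit.

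| Provision | Is the value used? |
|---|---|
| 8.2.3, first sentence of the rule | No, read literally |
| 8.2.2, mapping to weeks | Yes, it receives an analysis week |
| 8.2.2, end of treatment | Yes, if it is the last non-missing value |
| 5.6.4, clinically notable vital signs | Yes, expressly |
| 5.6.3, highest/lowest, TEMAV, maximum | Yes on its own wording; unscheduled visits not named |
| 5.6.5, QTc categories | Yes on its own wording; unscheduled visits not named |

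For 5.6.4 the contradiction with 8.2.3 is direct. For 5.6.3 and 5.6.5 the outcome depends on which provision governs, and the SAP does not say.

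**2. Does the mapping leave gaps?** The on-treatment windows in 8.2.2 are Days 2–25, 26–46, 47–67, 68–88, 89–119, 120–147 and 148–175. Each begins the day after the previous one ends. Every unscheduled or early-withdrawal assessment from Day 2 to Day 175 therefore receives a week, and 8.2.2 would have no reason to map such visits if 8.2.3 excluded them from all analysis.

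**3. Direction of the effect.** For subject *i*, let A_i be all postbaseline values in the treatment duration and S_i the subset from scheduled visits. Because S_i is contained in A_i, max(S_i) ≤ max(A_i) and min(S_i) ≥ min(A_i). For any open-ended threshold *c*, the number of subjects with max(S_i) > *c* cannot exceed the number with max(A_i) > *c*. This covers TEMAV, ALT or AST above 5 times ULN, bilirubin above 2 times ULN, and QTc above 450 or 500 ms. Hy's Law needs its criteria to be met at a visit, so fewer admitted visits cannot add a case. A bounded band, such as ALT between 3 and 5 times ULN, could gain a subject who drops out of the band above, but no open-ended count can rise.

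**4. Where it would bite.** Laboratory data have two scheduled on-treatment draws in the Core Study (Weeks 11 and 23) and untriggered unscheduled draws, so they are the main exposure. Vital signs are taken at every scheduled visit and have the express 5.6.4 provision.

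**5. Size.** The undercount depends on how many subjects have their only qualifying value at a visit that 8.2.3 would exclude. The documents do not give that number.

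**The case against.** The best defence is that 8.2.3 is a replicate-data rule, that its selection step concerns only actual values and changes, and that the specific table definitions in 5.6.3, 5.6.4 and 5.6.5 should prevail over a general handling convention. That is a reasonable reading and may be the intended one. It does not remove the problem: the first sentence of the rule is not limited, the SAP gives no order of precedence, and programming specifications and table shells are in separate documents (SAP 9 and 11).

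The defence does defeat several stronger readings that a reader might infer:

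- *Early-withdrawal values are lost altogether.* Not supported. 8.2.2 maps them to weeks, and one can be the end-of-treatment value.
- *The closest-assessment rule in 8.2.2 also strips the worst-value tables.* Not supported. Its paragraph is already confined to summaries by time point.
- *The Extension SAP has the same fault.* Not supported. It has the same mapping and time-point wording but no counterpart to the 8.2.3 sentence.
- *The ECGs left out are those most likely to be abnormal, because of note o.* Not shown. Before Week 23 the only scheduled ECG is at screening, and exclusion 12 bars clinically significant ECG abnormalities, so unscheduled ECGs before Week 23 should be rare.
- *The sparse schedule measures the loss.* It does not. The chance that a transient abnormality coincides with a planned test describes the visit schedule, and rewording 8.2.3 would leave it unchanged.
- *An affected child would appear nowhere.* Not supported. Laboratory abnormalities leading to intervention or withdrawal are adverse events (protocol 9.5.1.5.1), and SAP 5.6.3 flags markedly abnormal laboratory values in listings.

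**Conclusion.** The point holds as an internal contradiction with a known direction and an unknown size. Core SAP 8.2.3, read literally, conflicts with 5.6.4, with 8.2.2 and with the table definitions in 5.6.3 and 5.6.5. Applied that way, it would leave unscheduled values, mainly laboratory results, out of the worst-value tables and understate the incidence of marked abnormalities.

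This rests on two assumptions: that 8.2.3 is programmed as written, and that some subjects have their only qualifying value at an excluded visit. The documents establish neither, so it should not be reported that values have been lost or that the safety results are biased. It is still more than an editorial matter, because a stated rule on data feeding the primary endpoint supports two different counts. The Extension SAP analyses Core and Extension data together without such a rule, so the same Core laboratory value could count in one report and not in the other.

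**What to change.** Change Core SAP 8.2.3 in two ways:

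1. Limit the scheduled-visit and nearest-value rule to by-visit summaries of actual values and changes from baseline.
2. Add a statement such as: *TEMAV, highest/lowest shift, ALT/AST/bilirubin multiples, Hy's Law, clinically notable vital signs and QTc category tables use all postbaseline values within the treatment duration, including unscheduled, early-withdrawal and repeat measurements.*

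No change is needed to 8.2.2 or to the Extension SAP on this point. The cost is the SAP wording and a programming flag separating by-visit records from worst-value records. Reported incidence of marked abnormalities may rise slightly compared with a literal application of the present text.
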